526 obtained before any trial related procedures including screening procedures. The consent form,
527 potential risks and benefits, and the rights of research participants will be explained to the
528 participant by the investigators or research coordinator. Individuals will be asked if they have
529 questions, and a member of the research staff will answer questions. The principal investigator
530 will also be available at all times to answer questions that participants may have during the
531 consent procedure or during the time a participant is enrolled in the study. The consent form will
532 be completed in accordance with the IRB guidelines of Emory University. A signed copy of the
533 consent form will be provided to the participant and a copy will be placed in the file that is
534 maintained for each participant in the study office.
535

536 Informed consent will follow the procedure of Emory University Institutional Review Board.
537 Every potential participant will be informed in writing and verbally with the important and key

538 points of the study. One of the investigators or research coordinators will obtain a witnessed
539 informed consent prior to inclusion of a patient into the study.

540

541 The study will be conducted in accordance with the Declaration of Helsinki and will be
542 conducted in accordance with the ICH GCP guidelines. The sponsor-investigator will comply
543 with all applicable regulatory and legal requirements, ICH GCP guidelines and the Declaration
544 of Helsinki in obtaining and documenting the informed consent.

545

546 **STUDY SCHEDULE:**

FIRST PATIENT IN	2014 FEBRUARY
SCREENING	~2000
RANDOMIZED	280
LAST PATIENT RECRUITED	2020 MAY
LAST PATIENT IN (COMPLETED)	2020 DECEMBER
DATA ANALYSIS	DECEMBER 2020-JANUARY 2021
SUBMISSION TO CONGRESS OR JOURNAL	ADA 2021 MAJOR MEDICINE JOURNAL AND/OR DIABETES CARE

547

548 Flow Chart

Visit Type	Baseline Visit Hosp-prior to D/C	TC	Clinic visit	TC	TC	TC	Clinic visit	TC	TC	TC	TC	TC	TC	Clinic visit
Time-wks. ¹	0	2	4	6	8	10	12	14	16	18	20	22	24	26
Inf. consent	x													
Incl/excl criteria	x													
Random	x													
Withdrawal criteria		x	x		x		x		x		x		x	
Drug Compliance		x	x	x	x	x	x	x	x	x	x	x	x	x
Dose adjustment		x	x	x	x		x			x		x		x
Efficacy														
Vital signs	X		x				x							x
Phys Exam	X		x				x							x
Body wgt	x		x				x							x
Body measurements	X ²		x				x							x
BMI	x		x				x							x
HbA1c	X ³						x							x
Fasting BG	X ³		x				x							x
Collect 7-point profile			x				x							x
Chemistry (BMP or CMP)							x							
Safety														
Adv events	x	x	x	x	x	x	x	x	x	x	x	x	x	x
Hypoglyc.	x	x	x	x	x	x	x	x	x	x	x	x	x	x
Trial material														
Drug dispense	x		x				x							
Drug account	x		x				x							x
Remind 7-point profile prior next visit		x				x							x	

549

- 550 ¹ TELEPHONE CALLS AND OUTPATIEN VISITS CAN BE COMPLETED ± 7 DAYS.
- 551 ² TO BE COMPLETED WITHIN 7 DAYS AFTER D/C (IF NOT COMPLETED AT TIME OF DISCHARGE)
- 552 ³ OBTAINED FROM MEDICAL RECORDS (HBA1C \leq 3MONTHS)
- 553

554 **STUDY DRUGS AND MATERIALS:**

555 Clinical trial materials will be labeled and should be handled and stored according to the
556 respective hospital's regulatory requirements. After discharge, patients will be re-started on their
557 pre-admission OADs (except for DPP4-inhibitors and selected drugs in the presence of
558 contraindication, i.e., metformin and renal failure). Liraglutide or glargine will be provided
559 during the study.

560

561 **Study medication(s) / devices(s)**

562 Liraglutide 6.0 mg/mL solution for s.c. injection, provided in 3 mL prefilled pen.

563

564 **Storage and Drug Accountability of Study Medication(s)**

565 Liraglutide will be stored and dispensed by the research pharmacy at each institution. The
566 liraglutide prefilled pen and glargine will be stored in a refrigerator at a temperature between
567 +2°C and +8°C (+36°F and +46°F).

568 Once dispensed and in use (after first opening), the liraglutide prefilled pen can be stored for one
569 month at room temperature (+15°C to +30°C)/(59°F to 86°F) or in a refrigerator (+2°C to
570 +8°C)/(+36°F to +46°F). The liraglutide prefilled pen must be protected from all sources of light
571 and the pen cap should be kept on when the pen is not in use.

572

573

574 **Drug accountability:** The trial product will be dispensed to each subject as required according
575 to treatment group. The research/clinical staff will perform drug accountability by asking
576 patients to return all unused, partly used and unused cartridges and vials of liraglutide and
577 glargine insulin at each visit.

578

579 **Randomization and Blinding**

580 This is an open label randomized controlled trial. Patients will be randomized consecutively
581 using a computer generated randomization table provided by [name] at the Emory
582 School of Public Health. Patient will be randomized (block randomization) based on glucose
583 levels (BG>200 or BG<200). The randomization table will be mailed to each institution where a
584 member of the research team will be in charge of the randomization process and group
585 assignment.

586

587 **CONCOMITANT ILLNESSES AND MEDICATIONS:**

588 **Background medications:**

589

590 **Metformin.** Metformin is considered background medication (non-investigational medicinal
591 product) and will not be provided during the trial. The total daily dose of metformin prior to
592 admission will be restarted at hospital discharge (unless contraindicated = i.e., renal failure or
593 eGFR < 45 ml/min) with no dose adjustments occurring during the trial.

594
595
596
597
598
599
600
601
602
603
604
605
606
607
608
609
610
611
612
613
614
615
616
617
618
619
620
621
622
623
624
625
626
627
628
629
630
631
632
633
634

Sulfonylurea and Insulin secretagogues. Sulfonylurea treatment is considered background medication (non-investigational medicinal product) and will not be provided during the trial. The total daily dose of sulfonylurea prior to admission will be decreased at hospital discharge. During the study, no up-titration of sulfonylurea dosage will be allowed. Dose reduction of SU due to hypoglycemia may be allowed at the investigators discretion. In the event of hypoglycemia, the dose of sulfonylurea can be reduced or the drug can be stopped at the investigator's discretion.

Pioglitazone. Pioglitazone is considered background medication (non-investigational medicinal product) and will not be provided during the trial. The total daily dose of pioglitazone prior to admission will be restarted at hospital discharge. No dose adjustment or up-titration will occur during the trial; however, in the event of peripheral edema or signs of volume overload, the dose of pioglitazone can be reduced or stopped at the investigator's discretion.

ADVERSE EVENTS:

Definition: An AE is any untoward medical occurrence in a subject administered a product, and which does not necessarily have a causal relationship with this treatment. An AE is an unfavorable and unintended sign (including abnormal laboratory findings), symptom or disease temporally associated with the use of a product, whether or not considered related to the product. This includes events from the first trial related activity after the subject has signed the informed consent and until post treatment follow-up period as defined in the protocol. AEs include a clinically significant worsening of a concomitant illness and clinical laboratory adverse event (CLAE). An AE is either a serious AE (SAE) or a non-serious AE.

In this trial, an SAE is an experience that at any dose results in any of the following:

- Death
- A life-threatening experience
- Inpatient hospitalization
- Persistent or significant disability or incapacity
- Important medical events that may not result in death, be life threatening or require hospitalization
- Episodes of severe hypoglycemia will be captured as serious AEs.

Severity Assessment Definitions:

- Mild: Transient symptoms, no interference with the subject's daily activities
- Moderate: Marked symptoms, moderate interference with the subject's daily activities
- Severe: Considerable interference with the subject's daily activities, unacceptable

Relationship to Trial Product Assessment Definitions:

- Probable: Good reasons and sufficient documentation to assume a causal relationship

- 635 • Possible: A causal relationship is conceivable and cannot be dismissed
- 636 • Unlikely: The event is most likely related to an aetiology other than the trial product

637
638 Adverse events will be actively collected from the signing of the informed consent and in all
639 following contacts throughout the project. This includes events from all trial related activity after
640 the subject has signed the informed consent, and until the post treatment follow-up period, as
641 defined in the protocol.

642
643 **Outcome Categories and Definitions:**

- 644 • Recovered: Fully recovered or by medical or surgical treatment the condition has returned to
645 the level observed at the first trial related activity after the subject signed the informed consent
- 646 • Recovering: The condition is improving and the subject is expected to recover from the event.
647 This term should only be used when the subject has completed the trial
- 648 • Recovered with sequelae: As a result of the AE, the subject suffered persistent and significant
649 disability/incapacity (e.g. became blind, deaf, paralysed). Any AE recovered with sequelae
650 should be rated as an SAE
- 651 • Not recovered
- 652 • Fatal
- 653 • Unknown

654
655 **Reporting of adverse events:** All events meeting the definition of an AE must be collected and
656 reported. The events must be recorded in the AE form in a timely manner. During each contact
657 with the trial site staff (site visits and telephone contacts), the subject will be asked about AEs.
658 After the ICF is signed, all adverse events related to protocol procedures are to be reported.

659
660 The presence of SAE will be reported to the Emory IRB and Novo Nordisk within 24 hours by
661 fax or e-mail. A SAE is any adverse event from this study that results in one of the following
662 outcomes: death, initial or prolonged inpatient hospitalization, a life-threatening experience (that
663 is, immediate risk of dying), persistent or significant disability/incapacity, and events considered
664 significant by the investigator for any other reason.

665
666 **Reporting of pregnancies:** Female subjects who are pregnant or breast-feeding will not be
667 recruited in the study. Female subjects will be instructed to notify the investigator immediately
668 if they become pregnant during the trial. The investigator must report any pregnancy in subjects
669 who received liraglutide to the Emory IRB and Novo Nordisk. The pregnant subject will be
670 asked to provide information about her pregnancy, delivery and the health of her infant until age
671 one month. If the infant has a congenital anomaly/birth defect this must be reported and followed
672 up as a serious adverse event.

673
674
675

676 **Medical Events of Special Interest (MESI)**

677 Medical Events of Special Interest are those events thought to be [potentially] associated with
678 the investigational compound or disease under study. The investigators will collect information
679 on medical events of special interest including acute pancreatitis, cardiovascular events (heart
680 failure, acute myocardial infarction, and atrial fibrillation), malignancies, and medication errors
681 (e.g., incorrect dose of liraglutide or insulin).

682

683 **LIABILITY AND SUBJECT INSURANCE:**

684 **Financial Obligation.**

685 No additional cost to patients or to the institution will be incurred for research purposes. Patients
686 will not be billed for the laboratory work or any test that is being done only for study purposes.
687 Novo Nordisk will provide liraglutide at no cost to participants. Patients will be responsible for
688 the cost of their usual ongoing medical care, including procedures and/or non-study medications
689 that your doctor requires as part of your usual medical care.

690 **Research Injuries.**

691 If a patient is injured because of taking part in this study, [name] and investigators at each
692 institution, along with the medical facilities will make medical care available to the patient at the
693 patient's own cost. The only exception is if it is proved that the injury or illness is directly caused
694 by the negligence of an Emory or sponsor employee. "Negligence" is the failure to follow a
695 standard duty of care. Financial compensation for such things as lost wages, disability or
696 discomfort due to an injury related to the study is not available.

697

698 **Publication Plan:**

699 We anticipate completion of the study in October or November 2020. Data will be analysed in
700 December 2020. One abstract will be submitted to the 2021 American Diabetes Association
701 meeting and manuscript(s) will be submitted during the first six months of 2021.

702

703

704 **REFERENCES:**

- 705
- 706 1. **Kitabchi AE, Umpierrez GE, Murphy MB, et al.** Hyperglycemic crises in diabetes.
707 Diabetes Care. 2004;27 Suppl 1:S94-102.
- 708 2. **Umpierrez GE, Isaacs SD, Bazargan N, You X, Thaler LM, Kitabchi AE.**
709 Hyperglycemia: an independent marker of in-hospital mortality in patients with
710 undiagnosed diabetes. J Clin Endocrinol Metab. 2002;87(3):978-82.
- 711 3. **Finney SJ, Zekveld C, Elia A, Evans TW.** Glucose control and mortality in critically ill
712 patients. Jama. 2003;290(15):2041-7.
- 713 4. **Van den Berghe G, Wouters PJ, Bouillon R, et al.** Outcome benefit of intensive insulin
714 therapy in the critically ill: Insulin dose versus glycemc control. Crit Care Med.
715 2003;31(2):359-66.
- 716 5. **Pomposelli JJ, Baxter JK, 3rd, Babineau TJ, et al.** Early postoperative glucose control
717 predicts nosocomial infection rate in diabetic patients. JPEN J Parenter Enteral Nutr.
718 1998;22(2):77-81.
- 719 6. **Malmberg K, Ryden L, Efendic S, et al.** Randomized trial of insulin-glucose infusion

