96 to liraglutide or glargine with or without oral agents at hospital discharge.
97

98 **Endpoints:**

99 **Study Outcomes:**

100 The primary outcome of the study is to determine differences in HbA1c concentration at 26
101 weeks from discharge between liraglutide and glargine insulin therapy.
102

103 The secondary outcome is to compare differences between treatment groups in any of the
104 following measures during the 26 weeks following hospital discharge in patients with T2D:

- 105 • Self-measured blood glucose (SMBG) 7-point profiles
- 106 • Fasting and postprandial BG concentration
- 107 • Incidence rate and number of hypoglycemic events (<70 mg/dl) and severe hypoglycemic
108 events (<40 mg/dl).
- 109 • Percent of patients with 26 week HbA1c $<7.0\%$ and no hypoglycemia
- 110 • Percent of patients with 26 week HbA1c $<7.0\%$ and no weight gain
- 111 • Percent of patients with 12 week HbA1c $<7.0\%$ and no hypoglycemia
- 112 • Change in body weight and BMI

- 113 • Cardiovascular risk factors including changes in blood pressure, heart rate, and lipid
- 114 profile.
- 115 • Total daily dose of insulin
- 116 • Number of emergency room visits and hospital readmissions
- 117 • Acute renal failure during the 26-week follow-up defined as a clinical diagnosis of acute
- 118 renal failure with documented new-onset abnormal renal function (increment in
- 119 creatinine ≥ 0.5 mg/dL from baseline)

120
121

122 **Study type:**

123 The trial is a 26-week, randomized, open label-controlled two-armed, multi-center, multi-
124 national trial investigating the efficacy and safety of liraglutide versus glargine insulin in
125 medicine and surgical patients with T2D after hospital discharge.

126 We will recruit a total of 330 poorly controlled (HbA1c $\geq 7\%$ -10%) patients with T2D treated
127 with diet or oral antidiabetic agents (OAD) or on low-dose insulin therapy (TDD ≤ 0.4
128 unit/kg/day) prior to admission. Patients will be treated with a standard basal bolus insulin
129 regimen during the hospital stay. Prior to hospital discharge, patients will be randomized to
130 liraglutide or glargine with or without oral antidiabetic drugs. After discharge, a member of the
131 diabetes research team will contact patients via telephone call every 2 weeks to assess response
132 to therapy. In addition, patients will be asked to attend an outpatient clinic visit at 2 (optional), 4,

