133 12 and 26 weeks after hospital discharge. Recommendation on insulin dose adjustment will be
134 provided to patients at each telephone contact and clinic visits.

135
136 Recommendation for liraglutide dose escalation will be done every one or two weeks until the
137 maintenance dose of 1.8 mg is reached. Dose escalation can be extended over 2 weeks at the
138 discretion of the investigator in case of gastrointestinal adverse events. Liraglutide and insulin
139 will be add-on to the subject's pre-admission OAD regimen. Dose of OAD should remain
140 unchanged throughout the trial, however dose reduction of insulin and sulfonylurea is allowed
141 due to hypoglycemia.

142
143
144 **Study Groups:**

145 We plan to analyze a total of 280 patients (who receive study medication) with T2D at the time
146 of hospital discharge.

- 147
- 148 • Group 1. Liraglutide once daily in combination to OADs (n=140).
- 149
- 150 ▪ Group 2. Glargine once daily in combination to OADs (n=140).

151
152

153 **Study population:**

154 This will analyze 380 general medicine and surgical patients with a known history of T2D, age
155 18-80, treated with diet alone and/or oral antidiabetic agents including sulfonylureas, repaglinide,
156 nateglinide, DPP4s, SGLT2, or metformin as monotherapy or in combination therapy or on low-
157 dose insulin therapy (TDD ≤ 0.4 unit/kg/day) prior to admission. Subjects will be recruited from 5
158 medical centers in the United States. A total of 300 patients will be recruited at Grady Memorial
159 Hospital, Emory University Hospital and Emory Midtown hospital.

161 **Study Sites:** This study will be performed at Grady Memorial Hospital, Emory University
162 Hospital, Emory University Hospital at Midtown, and 3 institutions in the United States:

- 163 1. MetroHealth Medical Center, Cleveland (PI: [name].)
- 164 2. State University of NY at Buffalo (PI: [name].)
- 165 3. University of Miami, Florida (PI: [name].)
- 166 4. Sanatorio Guemes, Buenos Aires -Argentina (PI: [name])

169 **Inclusion Criteria**

- 170 1. Males or females between the ages of 18 and 80 years discharged after hospital admission
171 from non- ICU general medicine and surgical services (excluding gastrointestinal and
172 cardiac surgeries).
- 173 2. Admission HbA1c between 7% and 10%
- 174 3. Patients with T2D treated with diet alone or with oral antidiabetic agents as monotherapy or in

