175 combination therapy (excluding GLP1 receptor agonists) or on low-dose insulin therapy
176 (TDD ≤ 0.4 unit/kg/day) prior to admission.
- 177 4. Subjects with a hospital admission BG < 400 mg/dL without laboratory evidence of diabetic
178 ketoacidosis (serum bicarbonate < 18 mEq/L or positive serum or urinary ketones).
- 179 5. BMI > 25 Kg/m² and ≤ 45 Kg/m²

181 **Exclusion Criteria**

- 182 1. Age < 18 or > 80 years.
- 183 2. Subjects with stress hyperglycemia (BG > 140 mg/dL and HbA1c < 6.5%)
- 184 3. Subjects with a history of type 1 diabetes (1).
- 185 4. Treatment with GLP1 analogs during the past 3 months prior to admission.
- 186 5. Recurrent severe hypoglycemia or hypoglycemic unawareness.
- 187 6. Subjects with gastrointestinal obstruction, gastroparesis or those expected to require
188 gastrointestinal suction.
- 189 7. History of medullary thyroid cancer or multiple endocrine neoplasias
- 190 8. Patients with acute or chronic pancreatitis, pancreatic cancer or gallbladder disease.
- 191 9. Patients with clinically significant hepatic disease (cirrhosis, jaundice, end-stage liver
192 disease, portal hypertension) and elevated ALT and AST > 3 times upper limit of normal, or
193 significantly impaired renal function (GFR < 30 ml/min).

- 194 10. Treatment with oral or injectable corticosteroid (equivalent or higher than prednisone
195 5mg/day), parenteral nutrition and immunosuppressive treatment.
196 11. Mental condition rendering the subject unable to understand the nature, scope, and possible
197 consequences of the study.
198 12. Female subjects who are pregnant or breast-feeding at time of enrollment into the study.
199 13. Females of childbearing potential who are not using adequate contraceptive methods (as
200 required by local law or practice).

201

202 **Investigational drugs.**

203

- 204 • Liraglutide 6.0 mg/mL solution for subcutaneous (s.c.) injection. The solution will be
205 provided in 3 mL prefilled pen.
- 206 • Liraglutide will be provided to patients
- 207 • Glargine will be provided

208

209

210 **Withdrawal Criteria**

211

- 211 1. The subject may withdraw at will at any time.
- 212 2. The subject may be withdrawn from the trial at the discretion of the investigator due to a
213 safety concern or if judged non-compliant with trial procedures or included in contravention
214 to the inclusion and/or exclusion criteria.
- 215 3. Subject diagnosed with acute pancreatitis by clinical and/or radiographic criteria.

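### Metformin's dose is fixed for the whole trial, with no written exception if a patient reaches the protocol's own renal contraindication during follow-up

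*Combined protocol and SAP*

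**What the plan says.** The Metformin paragraph under Concomitant Illnesses and Medications restarts the pre-admission daily dose at discharge unless there is renal failure or "eGFR < 45 ml/min) with no dose adjustments occurring during the trial". Nothing in the paragraph qualifies the last part of that sentence.

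The next two paragraphs treat other oral agents differently. For sulfonylurea, if hypoglycemia occurs, "the dose of sulfonylurea can be reduced or the drug can be stopped" at the investigator's discretion. For pioglitazone the dose is also fixed, but "in the event of peripheral edema or signs of volume overload, the dose of pioglitazone can be reduced or stopped", again at the investigator's discretion.

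The Study type section gives the general rule. The oral-agent dose should remain "unchanged throughout the trial, however dose reduction of insulin and sulfonylurea is allowed", with hypoglycemia as the stated reason.

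The section on study drugs and materials mentions the renal issue again when it lists exceptions to restarting pre-admission agents after discharge: "contraindication, i.e., metformin and renal failure".

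The protocol also expects that renal function may fall during follow-up. The secondary outcomes include "Acute renal failure during the 26-week follow-up defined as a clinical diagnosis of acute" renal failure with a creatinine rise of at least 0.5 mg/dL.

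**The concern.** The protocol sets a renal limit for metformin and then applies it only once, at discharge. A patient discharged on metformin with an eGFR of 45 ml/min or more may later fall below 45 or develop renal failure. For that patient the text offers a fixed-dose rule and no renal exception. An investigator who follows the wording would not reduce the dose, and whether the drug may be stopped is left unsaid.

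What is at stake is the safety of individual patients and consistent handling across several sites. The sample size, the power and the primary HbA1c comparison are not in question.

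**Working it through.** No figure in the plan bears on this point, so the check compares the texts.

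**Step 1. The three background-drug paragraphs side by side.**

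| Agent | At discharge | During the trial | Safety exception in that paragraph |
|---|---|---|---|
| Metformin | Pre-admission dose, unless renal failure or eGFR below 45 ml/min | Dose fixed | None |
| Sulfonylurea | Reduced dose | No increase | Reduce or stop for hypoglycemia |
| Pioglitazone | Pre-admission dose | Dose fixed | Reduce or stop for edema or volume overload |

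Pioglitazone is the closest comparison. Its fixed-dose rule is almost the same as metformin's, and the authors still added an explicit exception. Metformin is the only one of the three for which this section names a contraindication, and the only one without an exception.

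**Step 2. Other text that might close the gap.**

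- Study type: the general rule names reductions for insulin and sulfonylurea only, and only for hypoglycemia.
- Group 1 and Group 2 treatment rules: contraindications are checked when metformin is started or oral agents are restarted at discharge.
- Study drugs and materials: the renal contraindication is tied to the restart after discharge.
- Protection against Risks: an oral agent may be reduced or discontinued, and metformin would be included, but the trigger is hypoglycemia.
- Pancreatitis text: suspect drugs are stopped if pancreatitis is suspected. The trigger is not renal.
- Withdrawal Criteria: "The subject may be withdrawn from the trial at the discretion of the investigator due to a" safety concern. This is an option to remove the patient from the trial. It is not a rule for holding one background drug.

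None of these gives a renal trigger during follow-up.

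**Step 3. Who is within reach of the gap.** Patients with GFR below 30 ml/min are excluded. Patients from 30 up to 45 may enter, but the Metformin paragraph already withholds the drug from them at discharge. That leaves patients discharged on metformin with eGFR of 45 or more whose renal function later declines. Patients newly started on metformin at discharge fall outside the Metformin paragraph, which speaks of the pre-admission dose. Only the general rule in Study type reaches them.

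**Step 4. Size.** The documents give no baseline eGFR distribution and no expected rate of renal events, so the number affected cannot be calculated. Only the timing can be read off. The flow chart, as extracted, shows on-study chemistry at week 12, which leaves 26 − 12 = 14 weeks of follow-up. With the 7-day window on each visit this is 25 − 13 = 12 to 27 − 11 = 16 weeks. That is how long the rule could apply after a scheduled result. It does not say how often the situation arises.

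**The case against.** The strongest reply is that nothing compels a patient to continue. The metformin sentence bars changes of dose, and the neighboring paragraphs mention reducing and stopping as separate acts, so stopping metformin is unaddressed and not prohibited. The general rule uses the word should, and its list of exceptions is plainly incomplete, since pioglitazone may also be reduced or stopped. Metformin is background treatment and not an investigational product, and restarting prior oral agents is left to usual care and clinical judgment. The study is bound by GCP and the Declaration of Helsinki, adverse events are reviewed at every contact, and abnormal laboratory findings count as adverse events. A competent physician would stop the drug.

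Most of this stands, and it keeps the point small. A reader might infer that the protocol forces patients to stay on full-dose metformin below the renal limit. The documents do not support that, because they never forbid stopping. A reader might also infer that stopping metformin means leaving the trial. No criterion says so, and the safety withdrawal criterion is optional.

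The reply does not remove the gap. Reducing the dose is squarely within the bar, and the pioglitazone paragraph shows the authors writing an explicit permission to stop immediately after a similar bar. The same physician would also act on edema or hypoglycemia without being told, yet those exceptions were written down.

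**Conclusion.** The point holds as a minor patient-safety correction. As written, the fixed-dose rule conflicts with the protocol's own metformin contraindication if renal function falls after discharge, and no other text supplies a renal exception.

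This rests on the wording alone and needs no numerical assumption. The number of patients affected cannot be derived, and in practice most investigators would probably stop the drug. A reader might go on to suspect bias in the HbA1c comparison. The documents give no basis for that, since they contain nothing on how often metformin would be changed or in which arm.

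**What to change.** In the Metformin paragraph, add after the fixed-dose rule: *however, if renal failure or eGFR < 45 ml/min develops during the trial, metformin will be held or stopped.* The wording should be mandatory. A clause that merely allowed reduction or stopping, like pioglitazone's, would let a patient stay on metformin below a level at which the protocol refuses to restart it.

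Add the same exception to the oral-agent rule in Study type, so that it also covers metformin newly started at discharge under the Group 1 and Group 2 rules. Record the change in the oral-agent dosage data already collected under Follow-up Care.

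The cost is one clause in each of two places, with no new visit, test or data field. The downside is that background therapy changes in a few patients, as the protocol already allows for sulfonylurea and pioglitazone.
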